## 8. Statistical software

Data is collected and entered on REDCap, and we will import the data into and conduct the analysis using STATA version 18.

We confirmed the need for the current study after presenting this evidence to Alberta Health and after completing systematic reviews of interventions to address these barriers. The systematic reviews assessed: 1) the effectiveness of reducing copayments for high-value drugs in people with chronic diseases and determined that reducing copayments may result in improved adherence to medical therapy (5); and 2) the impact of 11 quality improvement strategies for diabetes and determined that the most effective strategies were patient education and facilitated relay of information by patients to clinicians (6). Neither review could determine the impact of the interventions on clinical outcomes or costs – because available evidence consisted mostly of observational studies, or because trials were short-term and used surrogate endpoints.

2. Background and Rationale

What is the problem to be addressed?

Cardiovascular disease is the leading cause of death in Canada: Cardiovascular disease claimed over 69,500 lives in Canada in 2008 (7), most as a result of cardiovascular events, such as strokes and myocardial infarctions. Cardiovascular disease is also the leading cause of hospitalization for Canadians (8). Important risk factors for cardiovascular events include prior stroke or myocardial infarction, chronic kidney disease, heart failure, diabetes or hypertension (henceforth referred to simply as “chronic diseases”). These conditions lead to severe morbidity and cost the Canadian healthcare system over \$93 billion per year (1).

Many patients with chronic diseases do not receive guideline-recommended therapy: Lifestyle modification (i.e. weight loss, exercise, healthy diet, and smoking cessation) as well as adherence with pharmacologic management are particularly important in the management of patients with chronic diseases (9–13). In Alberta, our group has documented that 50% of Albertans with these chronic diseases are not receiving guideline-recommended drugs (statins), due to a combination of patient, provider and health system level barriers (3). Our recent survey of nearly 2,000 Western Canadians suggests that patient-borne cost of prescription drugs as well as patient and provider-level knowledge gaps, are major barriers to optimal medical management (3).

Cost-related barriers to medication adherence are relevant in Canada: While the Canadian publicly funded health care system funds hospital and physician care, patients are responsible for many of the direct costs related to outpatient management of their chronic conditions. Canada is unique among OECD countries given that not all citizens have insurance coverage for outpatient medications (14,15), and even those with supplemental insurance are usually subject to cost-sharing (i.e., copayments or deductibles) (16). This requires that patients pay a portion of the cost at the time of medication dispensing; typically a copayment of 20-30% of the total cost of the prescription (17) or deductibles which may be as high as 5-20% of household income (18). This may represent a substantial financial barrier, since our recent survey noted that 64% of patients with chronic diseases had an annual household income <\$55,000 (16). Furthermore, we found that the average self-reported annual out of pocket expenses on medications was \$782 (95%CI \$668-\$897). In Alberta, government-sponsored drug insurance is provided to people on social insurance and those aged over 65. People who do not meet age or income criteria can pay a premium to receive the government insurance. All Albertans over age 65, and those who pay a premium to receive Blue Cross coverage pay 30% copayment for drugs.

While copayments are meant to reduce inappropriate medication use, they may have important negative consequences. Being faced with costs at the time of medication dispensing may discourage patients from filling prescriptions, including for important preventive medications. Recent Canadian studies estimated that up to 10% of people experienced cost-related medication non-adherence (19), and that 23% of Canadians with chronic conditions have either skipped medication or failed to fill a prescription due to cost (20). In our recent survey of Western Canadians with chronic diseases, 8-20% identified financial barriers to drugs; and patients with these barriers were 30-55% less likely to use statins (16). Studies suggest that reducing copayments can improve adherence, though the impact on clinical outcomes is uncertain. One way to reduce the impact of these cost barriers is to provide full coverage for “high-value” medications (i.e., *defined as those medications that have been shown to confer important benefits in high quality studies, and/or provide good value for money*).

Other patient and provider-level barriers may also reduce appropriate medication use: Optimal management of chronic disease requires patient knowledge and a substantial degree of self-management (21) including adherence to outpatient medication regimens and lifestyle behaviour modifications. Our recent survey of Western Canadians suggested that 40% of chronic disease patients did not recall receiving counseling regarding lifestyle behavior modification, and of those who did, up to 70% of them did not follow the advice given (3).

Part of this may relate to the format of the message, which (when crafted and delivered by health care workers) may be factually correct without effectively changing behaviour. Alternatively, patients might receive and understand messages about the value of certain health behaviors but require assistance from a health provider to implement the needed changes. A prior systematic review examining the impact of 12 different chronic disease management strategies for patients with diabetes noted that two of the most effective strategies for improving glycemic control and blood pressure were *patient education*, and *facilitated relay of information to clinicians* (22). *Facilitated relay* is defined as clinical information transmitted by patients to clinicians by means other than the existing medical record (22); the expectation is that clinicians act on the information to change patient management. In the ACCESS trial, the *facilitated relay* will involve patients providing personalized recommendations on the medications that should be used to treat their chronic diseases (provided to the patient within study educational materials) to their regular health care provider. Recommendations are based on contemporary clinical practice guidelines and use strategic marketing practices targeting patients not receiving guideline-concordant medications at study baseline.

3. Trial Objectives

Primary Objective:

To determine the effect of two novel interventions; (i) a value-based formulary which eliminates copayment for select high-value medications (proven to prevent heart attacks, stroke, and hospitalizations); and (ii) a comprehensive patient education program aimed at lifestyle modification and optimal drug use, combined with relay of information on medication use, on the risk of adverse clinical outcomes (mortality, heart attack, stroke, need for coronary revascularization, and chronic disease related hospitalizations) over three years.

Secondary Objectives:

To determine the effect of two novel interventions on medication adherence, overall quality of life, and health care costs.

4. Trial Methods

4.1. Trial Design

The ACCESS trial is a parallel, open-label factorial 2X2 randomized controlled trial with blinded end-point evaluation. Given the nature of these interventions, patient blinding is not possible.

4.2. Trial Interventions

- 1. Elimination of copayments:** (reduction from 30% to 0%) for select high-value preventive medications by enrolling patients in a new Alberta Blue Cross drug coverage plan which was designed by the study team, including leaders at Alberta Health specifically for ACCESS (see letter of support, [name]). Since these patients either have or are at high risk of cardiovascular disease, the medications include statins, beta blockers, ACE-inhibitors, angiotensin receptor blockers, calcium channel blockers, diuretics, anti-platelet agents,

anticoagulants, oral hypoglycemics, insulin and smoking cessation aids (23) (see Appendix II). These formulary changes will be operationalized by transferring patients allocated to this intervention to a new government-sponsored Alberta Blue Cross formulary plan with updated payment rules.

2. **Patient education strategy on lifestyle modification and medication use** designed in collaboration with a leading marketing firm (see letter of collaboration, Emergence) and based on our recent survey of Western Canadians (3,4,24). The education program will be combined facilitated relay of information on patient medication use to their health care provider. Patients who are not using guideline-recommended therapy (including statins) at baseline will be given personalized recommendations to take to their usual clinician, aiming to increase the appropriate use of beneficial medications. Dissemination will occur by email invitations to access the personalized study website portal or regular post, depending on preferences of the participant (elicited at baseline). Personal health information will not be sent within emails. For any educational messages tailored to a specific patient's health information (as provided by them within baseline information forms), patients will be directed to log on to a secure password protected website.

Control patients for the two intervention arms will continue to receive all medications as per their usual coverage and/or will receive annual mailings of general educational materials about chronic disease.

4.3. Primary Outcomes

Outcomes of relevance to patients with chronic disease: When management of chronic disease is suboptimal for extended periods, patients may be hospitalized for complications (25). While myocardial infarction, stroke, and the need for revascularization are the classical complications (and are components of our primary outcome), hospitalization for chronic disease-related ambulatory care sensitive conditions are also relevant, since these complications can serve as a proxy for poor control of chronic disease. Ambulatory care sensitive conditions (ACSC) are those for which “timely and effective outpatient care, including use of appropriate medications, can help to reduce the risk of hospitalization by preventing the onset of an illness or condition, or managing a chronic disease” (26). While several agencies have examined what constitutes an ACSC for the chronic diseases under study, the most applicable definition of ACSC for cardiovascular diseases, diabetes and hypertension using a Canadian context is from CIHI (2009). Since this does not include hospitalizations for CKD-related ACSC, this list was taken from a recent Canadian study (27). Importantly, these potentially preventable hospitalizations are clinically relevant to patients and represent an important economic burden for the system (28), which might be avoided through interventions which optimize patient management (29,30).

Primary Outcome: The primary outcome is the composite rate of any of the following: all-cause mortality, myocardial infarction, stroke, coronary revascularization (coronary artery bypass grafting, angioplasty, or coronary stenting), and hospitalizations for chronic disease-related ambulatory care sensitive conditions. Given that an individual may have

multiple events during the follow-up period, we have chosen to use a rate outcome rather than a simple binary composite outcome.

4.4. Secondary Outcomes

- 1) each individual component of the primary endpoint
- 2) medication adherence for selected medications as defined below
- 3) overall quality of life as measured by the Euroqol EQ5D-5L
- 4) the cost of the interventions and other costs relevant to the health care system assessed in a concurrent economic evaluation.

4.5. Tertiary Outcomes (some to be reported in secondary manuscripts)

- A) Body-mass index
- B) Smoking status
- C) Prescription of indicated medications
- D) Treatment satisfaction
- E) Medication Needs-Concerns
- F) General barriers to care
- G) Financial barriers to care
- H) Health literacy
- I) Self-reported general health
- J) A1C (among those with diabetes)
- K) Albuminuria
- L) Serum Creatinine/estimated GFR
- M) LDL-cholesterol

4.6. Timing of outcomes as assessments

The primary outcome data was ascertained through administrative health data held within the province of Alberta, including linked datasets such as: laboratory data, pharmacy dispensation data, acute care data, outpatient physician claims data, and demographic data. Participants were followed for a minimum of 2.5 years from the time of randomization through until March 30, 2021. This data will be available as of early 2022.

Self-reported outcome measures were obtained via electronic and paper-based surveys which were sent to participants 6-, 18-, and 33-months after randomization.

4.7. Randomization

The University of Calgary Clinical Research Unit developed the computer-generated randomization scheme within REDCap.

Randomization was completed using random small (<8) variable permuted blocks. This method will ensure robust allocation concealment. Randomization was stratified based on: age (</≥70 years); gender (man/woman); and low household income status (defined by household-size specific Low-Income Cut-offs).

4.8. Sample Size

Using the cohort of 170,000 Albertans described above, we estimated the annual event rate for this study reflecting the expected age distribution of enrollees. We found that this cohort of patients at high cardiovascular risk had a 26% risk of myocardial infarction, stroke, death or chronic disease-related hospitalization over a three-year observation period (Appendix VII). However, the endpoint in our primary outcome is not a binary event (many individuals had multiple events during the observation period), and so we have chosen to include recurrent events in our sample size calculation. In our administrative dataset, the rate of the primary outcome (MI, stroke, revascularization, death, or chronic disease-related hospitalization) is 14 per 100 participant years (Appendix VII).

We estimated the sample size required for Poisson regression analysis (31), using the following parameters: an annual event rate of 14 per 100 participant years, a minimal clinically important difference of a 12% relative risk reduction, $\alpha=5\%$, 80% power, allocation ratio of 1:1, average follow up of 3 years and presumed 1 percent per year loss to follow-up (32). The estimated total sample size required for the study was 4714 patients (4667 +1% of individuals who are expected to move out of province during the study) (Appendix VIII). Our sample size calculation assumed that there will not be an important interaction between our two interventions. To verify this assumption, we generated simulations using interactions of 25% and 50%. At both of these levels of interaction, with our current projected sample size, the effect on study power was negligible.

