10.2. Distributional Assumptions and Outlying Responses

There is the potential that some participants will have had repeated hospital encounters and excessive costs. If the number of these participants is imbalanced between the randomization groups, these outliers have the potential to skew results. In order to address this potential concern, we plan to conduct a secondary analysis in which the participants in the top 1% of encounters/costs will be excluded.

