10.4. Analysis Methods- Primary Outcome

Consistent with an intention-to-treat analysis, we will categorize all participants by their randomization group, regardless of compliance (intention-to-treat), in our primary analysis. For those participants who are no longer actively receiving the self-management intervention or completing follow-up surveys, as permitted by CHREB, we plan to use available health administrative data until the time of death or outmigration from the province.

A Poisson model will test the main effects of the impact of the interventions on the rate of the primary outcome. This technique was chosen as individuals may experience multiple outcomes prior to the end of the study period, therefore we will account for both number of events and varying observation time within the Poisson model (by using an offset to account for losses to follow-up). The likelihood ratio test will test a negative binomial regression model within the Poisson model to examine for the presence of overdispersion. If present, negative binomial models will be used.

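### The 80% power in section 4.8 rests on Poisson variance, but that section's own event figures point to overdispersed counts, so 80% power for a 12% reduction is not supported under the planned 3-year design

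*Combined protocol and SAP*

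**What the plan says.** Section 4.8 of the combined protocol and SAP describes the calculation as follows: "We estimated the sample size required for Poisson regression analysis (31), using the following parameters". The parameters are 14 events per 100 participant-years, a 12% relative reduction, 5% alpha, 80% power, 1:1 allocation, average follow-up of 3 years and 1% loss per year. The result is 4667, raised to 4714. No dispersion parameter is listed. The only robustness check described concerns interaction between the two interventions.

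The same section gives two descriptions of the planning cohort, both referred to Appendix VII. As a proportion of people, the cohort "had a 26% risk of myocardial infarction, stroke, death or chronic disease-related hospitalization over a three-year observation period". As a rate, "the rate of the primary outcome (MI, stroke, revascularization, death, or chronic disease-related hospitalization) is 14 per 100 participant years". It adds that "many individuals had multiple events during the observation period". The age weighting is attached to the rate: "we estimated the annual event rate for this study reflecting the expected age distribution of enrollees". The section does not say whether the 26% has the same weighting.

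Elsewhere, section 10.2 says: "There is the potential that some participants will have had repeated hospital encounters and excessive costs". Section 10.4 plans a Poisson model with a likelihood ratio test for overdispersion: "If present, negative binomial models will be used". On follow-up, section 4.6 says: "Participants were followed for a minimum of 2.5 years from the time of randomization through until March 30, 2021". Section 7.1 gives 4768 randomized and a 30-month enrolment period.

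**The concern.** The risk and the rate describe the same cohort, so together they say something about the shape of the counts. If fewer people have events than a Poisson count with that mean would produce, events are concentrated in some people and the variance exceeds the mean. The log rate ratio is then less precise than the calculation assumed. The plan allows for this in the analysis (section 10.4) but not in the sample size.

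What is at stake is how a null result is read. The SAP's introduction (section 2) reports that removing copayments did not improve clinical outcomes, and SAP section 5.6 repeats 4714 as the calculated size. A reader who takes 80% at face value would give that null more weight against a 12% reduction than the design supports. Moving to a negative binomial model protects the type I error but does not restore power.

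**Working it through.** **1. Reproduce the stated N.** Inputs from section 4.8: rate 0.14 per year, 3 years (mean 0.42 per person), rate ratio RR = 0.88, 1:1. Alpha is taken as two-sided. With variance equal to mean:

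N = [1.96·√4 + 0.8416·√(2 + 2/0.88)]² / (0.42 × (ln 0.88)²) = 4666.97, that is 4667. Then 4667 × 1.01 = 4714.

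A one-sided test gives 3686, an unpooled Wald formula 4887, and a rate-difference formula 4880. A dispersion factor above 1 would raise N. Appendix VIII is not in the text supplied, but the exact match makes a hidden allowance implausible.

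**2. Compare the two cohort figures.** Under Poisson, the any-event risk is 1 − exp(−0.42) = 34.3%. If deaths cut the cohort's mean follow-up to 2.8 years (assumption), it is 1 − exp(−0.392) = 32.4%. The stated risk is 26%.

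**3. Could revascularization close the gap?** The rate includes it and the 26% does not. Under Poisson, 26% corresponds to −ln(0.74) = 0.301 events per person, or 10.0 per 100 participant-years (10.8 at 2.8 years). Revascularization would then have to supply 3.2-4.0 of the 14 events, or 23-28%. It would also have to add 6-8% of the cohort who had no other event. The documents give no figure that supports this.

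**4. Power with negative binomial counts.** The dispersion k solves ln(1 + kμ)/k = −ln(1 − p). Here p is the any-event risk, μ = 0.14 × F, and F is the cohort's mean follow-up (3.0 or 2.8 years). The variance of the log rate ratio is the sum over arms of (1/(rate × T) + k)/n, where T is the trial's follow-up and n the number per arm.

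Example with p = 26%, F = 3.0, T = 3 and n = 2357: k = 2.10, so the control arm's variance is 1 + 2.10 × 0.42 = 1.88 times its mean. The variance of the log rate ratio is (1/0.42 + 1/0.3696 + 2 × 2.10)/2357 = 0.00394, and the standard error is 0.0628. Then 0.1278/0.0628 − 1.96 = 0.077, which is 53.1% power.

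Each cell below gives power (%) from the Wald formula, then from the step 1 formula with negative binomial variance.

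| Any-event risk | F (years) | k | N = 4714, T = 3 | N = 4768, T = 3.75 |
|---|---|---|---|---|
| 26% | 3.0 | 2.10 | 53.1 / 54.4 | 58.3 / 59.5 |
| 26% | 2.8 | 1.68 | 56.9 / 58.4 | 62.9 / 64.2 |
| 28% | 3.0 | 1.44 | 59.4 / 61.0 | 65.8 / 67.2 |
| 28% | 2.8 | 1.05 | 63.9 / 65.6 | 71.0 / 72.5 |
| 30% | 3.0 | 0.89 | 65.8 / 67.5 | 73.2 / 74.7 |
| 30% | 2.8 | 0.52 | 70.8 / 72.6 | 78.8 / 80.3 |

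With k = 0, the two formulas give 78.6% and 80.4% at N = 4714 and 3 years, so the choice of formula accounts for about 2 points.

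The reduction detectable with 80% power is 13-16% in the planned design and 12-15% at 3.75 years.

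**5. Does this depend on the negative binomial?** With mean 0.42 and risk 26%, affected people average 0.42/0.26 = 1.62 events. The variance is smallest if each has one or two events: 0.26 × (0.385 + 4 × 0.615) − 0.42² = 0.564, or 1.34 times the mean. Power is then 66-68%. A zero-inflated Poisson fitted to the same two figures gives 59-61%. Simulation at these two figures (6,000 trials, 2357 per arm, robust variance) gave 52.8% for the negative binomial, 59.7% for the zero-inflated Poisson and 66.7% for the smallest-variance case. Type I error was 5.2-5.5%.

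**6. Actual follow-up.** A 2.5-year minimum plus half of a 30-month enrolment is 3.75 years, assuming even accrual and before death or outmigration. November 2015 to 30 March 2021 is 5.41 years. That would give a mean of (5.41 + 2.5)/2 = 3.95 years, or 5.41 − 1.25 = 4.16 years if enrolment lasted 30 months. At 4.0-4.2 years power is 59-83%.

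**7. Break-even.** For 80% power, the any-event risk of the full composite must be 32-34% at 3 years (essentially pure Poisson) or 30-32% at 3.75 years.

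**The case against.** The strongest objection is that the 26% and the 14 per 100 are not like for like. One omits revascularization, and the age weighting may differ. Step 3 puts the whole gap on revascularization. If age weighting alone had raised the rate by 20% (an assumption; neither size nor direction is given), revascularization would need to supply only 8-14% of events. At 30% it would need 0-7%. This stands as a limit on how exactly the shortfall can be sized, and only Appendix VII can settle it. It does not make the stated 80% supported.

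The supporting wording is also weaker than the numbers. A Poisson mean of 0.42 already puts 6.7% of people at two or more events, section 10.2 speaks only of a potential, and section 10.4 plans a test rather than forecasting its result. The case therefore rests on 26% against 34.3%.

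The completed trial was slightly larger and followed for longer than planned. That stands too: power reaches 80% at the favourable end, so for the trial as run a shortfall is plausible but not shown.

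Finally, the plan already has a negative binomial fallback and 95% confidence intervals (section 5.1), and recruitment is over. These protect the analysis and help the reader, but they do not correct the stated power. Power for the prespecified 12% reduction is also not the discredited power for an observed effect.

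**Conclusion.** The concern holds. The arithmetic behind 4667 and 4714 is right; the fault is an unstated assumption that variance equals mean, which the section's own figures contradict if taken at face value. That no dispersion allowance entered the calculation is as good as certain. For the planned design, negative binomial power for a 12% reduction is 53-73% across any-event risks of 26-30%. The smallest variance compatible with 0.42 events per person and a 26% risk still gives only 66-68%. For the trial as run it is 58-80% at about 3.75 years. These ranges assume the same age mix for risk and rate, a cohort mean follow-up of 2.8-3.0 years and even accrual. The direction is well supported, but the exact size depends on Appendix VII.

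**What to change.** Keep N and the analysis in section 10.4, and add to section 4.8 text along these lines:

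> The sample size was calculated with Poisson variance and no allowance for overdispersion. With the dispersion and any-event risk of the full composite (including revascularization, same age weighting) from the Appendix VII cohort, and actual mean follow-up of [x] years, N = 4768 gives [y]% power for a 12% reduction and 80% power for a [z]% reduction. Null results will be interpreted from the 95% confidence interval.

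The cost is one recalculation from data the team already holds and a few sentences. It needs no extra participants and no change of method. The stated power will probably become less favourable.

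As a clerical matter, the loss wording in section 4.8 (1% per year, then 1% over the study) and in SAP section 5.6 should agree. N need not change: 1% lost at the end of each year gives 4667/((1 + 0.99 + 0.9801)/3) = 4714 on person-time, the same as 4667 × 1.01.

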4.13. Trial Comparisons

The impact of the two interventions will be conducted independently of one another. We will compare each intervention arm to those who did not receive that specific intervention.

5. Statistical Principles

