5.1. Confidence Intervals and P-values

In all our analyses, we will calculate 95% Confidence intervals around all point estimates and will calculate p-values using appropriate statistical tests. We will consider our alpha value to be 0.05.

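### Minor: the sample size in section 4.8 is a two-arm calculation that gives the whole comparator margin the usual-care event rate, although about half of it is allocated the other intervention

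*Combined protocol and SAP*

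**What the plan says.** All references are to the combined protocol and SAP unless stated otherwise.

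- **Base rate (4.8).** The figure is introduced with "In our administrative dataset, the rate of the primary outcome" and is 14 per 100 participant-years, from a large Albertan cohort. Nothing suggests that this cohort had the trial's new formulary plan or its education programme.
- **Inputs to the calculation (4.8).** The calculation takes "an annual event rate of 14 per 100 participant years, a minimal clinically important difference of a 12% relative risk reduction", with alpha 5%, "80% power, allocation ratio of 1:1", and "average follow up of 3 years and presumed 1 percent per year loss to follow-up". The result is 4667, raised by 1% to 4714.
- **Design and comparison (4.1, 4.13).** The trial is a 2x2 factorial, and 4.13 states: "We will compare each intervention arm to those who did not receive that specific intervention". This is a comparison at the margins.
- **Factorial allowance (4.8).** Only interaction is discussed. None is assumed, and simulations with interactions of 25% and 50% are reported as barely affecting power. Nothing is said about a main effect of the other intervention on the comparator rate.

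**The concern.** In a marginal comparison, the group without intervention A consists of participants with neither intervention and participants with B alone, in roughly equal numbers. If B works, that group has fewer events than a usual-care cohort. The group with A is diluted in the same proportion. With multiplicative effects the rate ratio for A is unchanged, but both margins supply fewer events, and the precision of a Poisson rate ratio depends on the number of events.

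The absence of interaction does not remove this. Dilution is a consequence of B's main effect and is present at zero interaction and with pure Poisson counts.

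What is at stake is the accuracy of the stated 80%. It is given without its condition, and the primary objective in section 3 is to determine the effects of both interventions on events. A reader who sees interaction discussed may suppose that the factorial structure has been fully allowed for.

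**Working it through.** **Inputs.** Comparator rate λ = 0.14 per year, rate ratio RR = 0.88, T = 3 years, power 80% and 1:1 allocation, all from 4.8. Alpha is 0.05 (5.1: "We will consider our alpha value to be 0.05"). Sidedness is not stated. I take two-sided, in line with 5.1 ("we will calculate 95% Confidence intervals around all point estimates") and because it reproduces the plan's figure. The effect of the other intervention, RR_other, is not given. I assume 0.88 and show a range.

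**Formula.** Sample size for Poisson regression with a balanced binary covariate:

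N = [z₀.₉₇₅·√4 + z₀.₈₀·√(2 + 2/RR)]² / (T·λ·(ln RR)²)

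**Step 1: reproduce the plan.**
- Numerator: (3.9199 + 1.7397)² = 32.031
- Denominator: 3 × 0.14 × (ln 0.88)² = 3 × 0.14 × 0.016341 = 0.0068634
- N = 4666.97, so 4667. Then 4667 × 1.01 = 4713.7, so 4714.

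The alternatives tried do not give 4667: one-sided 3685, Wald log rate ratio 4886, rate difference 4880, pooled null variance 4872, square-root 4875. The match therefore identifies both the formula and the undiluted rate of 0.14 in the comparator group.

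**Step 2: dilute the comparator margin.** With half allocated the other intervention and no interaction:

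λ = 0.14 × (1 + RR_other)/2 = 0.14 × 1.88/2 = 0.1316

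- Denominator: 3 × 0.1316 × 0.016341 = 0.0064516
- N = 4964.9, so 4965. That is 298 more than 4667 (+6.4%).

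**Step 3: power at the planned size.**

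Power = Φ{[√(N·T·λ)·|ln RR| − 3.9199] / √(2 + 2/RR)}

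At N = 4667 and λ = 0.1316: (5.4872 − 3.9199)/2.0671 = 0.758, so power is 77.6%.

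| RR_other | Comparator rate per 100 | Power, N = 4667 | Power, N = 4714 |
|---|---|---|---|
| 1.00 | 14.00 | 80.0% | 80.4% |
| 0.95 | 13.65 | 79.0% | 79.4% |
| 0.90 | 13.30 | 78.0% | 78.4% |
| 0.88 | 13.16 | 77.6% | 78.0% |
| 0.80 | 12.60 | 75.8% | 76.2% |

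The 4667 column corresponds to 4714 enrolled with the 1% lost. The last column lets all 4714 contribute three years. The two should not be mixed.

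**Cross-check.** A Poisson simulation of the four cells with a Wald test (200,000 runs, N = 4667) gave 78.2% with RR_other = 1 and 75.8% with RR_other = 0.88. The level is a little lower than the formula's, but the loss is again about 2.4 points.

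**Step 4: sensitivity to follow-up.** With both interventions at 0.88, 80% power needs a mean follow-up of about 3.19 years at 4667, or 3.16 years at 4714. If mean follow-up were 4 years (assumed), power would be 87.9% at 4667 and 88.2% at 4714, against 89.7% and 90.0% without dilution.

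**The case against.** The strongest reply has four parts.

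1. **The 12% is a detection threshold for one comparison, not a forecast that both interventions achieve it.** This stands. A second effect of 12% is my assumption, and the loss shrinks with a weaker one. That is why a range is needed. It does not remove the point, because the 80% still corresponds to one end of that range.

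2. **The trial as run is not the trial in the formula.** A reader might infer that 80% is lost as soon as the other intervention has any effect, or that the trial was underpowered. The documents support neither. The condition is exact only at 4667 participants and 3 years. Section 7.1 reports 4768 randomized. At that number and 3 years, power stays at 80% or more until RR_other falls below about 0.958 (about 0.977 after a 1% loss). Follow-up matters more. Section 7.1 gives a 30-month enrolment period, with calls from November 2015, and 4.6 follows participants to 30 March 2021. With even accrual (assumed), that averages about 4 years. Section 3 does speak of three years, so the window is itself ambiguous, and any restated power must name it.

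3. **The interaction simulations may have covered this.** Simulating interaction in a 2x2 requires a main effect for each intervention, so scenarios with both active may have been run. The text does not report the main effects used, and Appendices VII and VIII are not in the text available. This remains open, but the 4667 itself contains no such adjustment.

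4. **Section 5.6 of the separate SAP would need the same correction.** A reader might infer this because that section repeats the 4714. It does not follow. That SAP analyses beliefs about medication, self-efficacy and adherence, and power for the event rate has no bearing on those outcomes.

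**Conclusion.** The point holds as a minor one, confined to section 4.8. The 4667 applies the usual-care rate to the whole comparator margin, while the planned comparison places about half of that margin on the other intervention. On the plan's own formula and 3-year window, power at 4667 falls from 80.0% to 77.6% if the other intervention also reduces events by 12%, and lies between 79.0% and 75.8% for reductions of 5% to 20%.

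These figures assume 1:1 allocation to each intervention, multiplicative effects without interaction, a two-sided 5% test and pure Poisson counts. Longer mean follow-up raises power. Overdispersion, for which 10.4 plans negative binomial models, lowers it. No estimate, interval or test in the analysis is affected.

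**What to change.** Replace the bare power statement in 4.8 with wording such as:

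*With 3 years of follow-up and Poisson counts, 4667 evaluable participants give 80% power for a 12% reduction by one intervention if the other has no effect on events. If the other also reduces events by 12% with no interaction, the marginal comparator rate is 13.2 per 100 participant-years and power is about 77.6% (about 79.0% if the other reduces events by 5%, 75.8% if by 20%). Power is higher if mean follow-up exceeds 3 years (about 88% at an assumed 4 years with both interventions at 12%) and lower under overdispersion.*

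If the interaction simulations gave both interventions a main effect, add the values used. Enrolment, conduct, analysis and section 5.6 of the separate SAP stay as they are. The cost is a few sentences and a slightly less favourable stated power at 3 years.
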